**Overview of the design.** The study conducted will be a longitudinal randomized block RCT with repeated measures (beginning with screening prior to 19 weeks, group prenatal care in both groups (COPE-P intervention group and PregnancyPlus attention control group) from  $16 \pm 2$  to  $31 \pm 2$  weeks and ending at 6 months postpartum). We will block on race/ethnicity to ensure equal numbers of Hispanic and Black women in the COPE-P and PregnancyPlus groups. There will be a total of 30 groups over the course of the study. There will be 22 English speaking groups and 8 Spanish-speaking groups. We will consent and screen up to 700 women, knowing that approximately half will screen out. In order to achieve our target of 182 Black or Hispanic women who complete the study, and accounting for a 30% attrition rate, we will enroll up to 236 women who screen in at Jacobi Medical Center. Four groups (of at least six women per group) will run in each 18-week time segment (COPE-P intervention is six sessions each three weeks apart). The PregnancyPlus group also will have six group prenatal care sessions each three weeks apart. Each session is 1 hour and 30 minutes to 1 hour and 45 minutes in length. Each group within the 18-week time segment will be randomly assigned (using a sealed envelope technique) as either a COPE-P or PregnancyPlus group. At Jacobi Medical Center in Bronx, NY, for each 18-week time segment, there will be two control groups and two intervention groups. The intervention and attention control groups programming will be delivered in Group Prenatal Care methodology which begins in the second trimester consisting of at least 6 women per group. Participants (18 – 40 years) will be screened prior to their 19th week of pregnancy and recruited into the study from the antepartum clinic.

If a participant does not screen into the study, she will be thanked for her time and interest and paid \$10.00 for her participation in the screening process.

07/30/2021

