**PregnancyPlus Attention Control Group:** At each group session, the PregnancyPlus attention control group will receive the prenatal care described under standard care performed by certified nurse midwives. Additionally, each week for six weeks, they will discuss a pamphlet designed for patient education by ACOG. These six pamphlets are: 1) Nutrition during pregnancy 2) Exercise during pregnancy 3) Obesity and pregnancy 4) Exercise after pregnancy 5) Breastfeeding your baby 6) Routine Tests during Pregnancy. At each group prenatal care session, routine obstetric assessment (blood pressure, pulse, weight, BMI, urinalysis for glucose and protein, auscultating fetal heart tones, and uterine size assessment) will be performed. Routine discomforts of pregnancy, smoking cessation, and danger signs of pregnancy will be discussed. Women will return to receiving individualized standard prenatal care at the end of the 6 sessions. [name] will conduct the training of the attention control group midwives and [name] will conduct the training of the intervention group midwives. The same protocol for assessing fidelity will be used for COPE-P and PregnancyPlus.

Different care providers will run the COPE-P and PregnancyPlus groups, assuring that there is no carryover effect of the intervention into the control group.

In addition to baseline assessments, at the end of the 18-week timeframe and at their last group prenatal care session, all women will complete the GAD-7, PSS, EPDS, a 24 hour diet recall, the Healthy Lifestyle Behaviors Scale and the Healthy Lifestyle Beliefs Scale. Fitbit data and weight also will be obtained. In the intervention group, participants also will complete the COPE-P evaluation. This data will be **T1**, and will be collected at approximately 31 weeks gestational age. For women who miss this visit, data will be collected at the next scheduled prenatal visit. Participants will be compensated \$30 for their study participation.

Three months after the intervention (approximately 4-6 weeks postpartum - **T2**), all women will be contacted and will once again complete all measures, as well as an infant data form, at the routine postpartum visit. Participants will receive \$40.00 for their participation.

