the delivery of emergency and trauma services, has developed an image of excellence as a provider of choice subspecialty care, and is widely recognized for its devotion to the health care needs of the large and diverse community it serves. The Bronx population represents a wide range of racial and ethnic diversity with 43.4% of the population being African-American and 55% of the population being Hispanic, adding up to more than 100% as Hispanics may be of any race and are also included in the applicable race category by the U.S. Census Bureau (2015). Jacobi Medical Center is an urban medical center, which serves a population of 1.3 million. The Obstetrics Division serves the region as demonstrated by over 12,000 clinic visits as well as approximately 2,000-plus hospital discharges per year. There were 1960 live births at Jacobi Medical Center during 2015 with 1373 of these births to Black and Hispanic women.

Obstetrical care is provided by 22 licensed midwives at Jacobi Medical Center as well as by over 40 obstetricians. There are adequate numbers of bilingual licensed midwives to work with Co-Investigator [name], CNM, RN to provide group prenatal care. There is an excellent working relationship between obstetrical and pediatric care providers and both obstetrical and pediatric care providers are interested and supportive of this study.

Jacobi Medical Center offers a number of other resources to its obstetrical patients receiving care in the Women's Health Practice. There are two Women's Health Patient Educators, who provide a weekly class series, with a new curriculum each month covering topics like childbirth education, infant safety and postpartum care. Women are encouraged to attend all of them starting in the 7th month of pregnancy. The Midwifery staff offer monthly Childbirth Education classes. There are two full-time IBCLC-certified Lactation Consultants available to patients in both the group and individual setting to assist with the initiation and continuation of breastfeeding. Jacobi has a specialized Adolescent Obstetric Practice to meet the needs of young mothers-to-be and Family Planning Services. Pregnant women and new mothers, who meet income eligibility criteria, are assessed by a healthcare professional for WIC eligibility which would provide them access to nutrition advice, breastfeeding support, nutritious food, and other services.

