All women in this study will receive 6 sessions of group prenatal care beginning at 16 weeks gestation ( $\pm 2$  week) and ending at 31 weeks ( $\pm 2$  week) according to previously described randomization into COPE-P intervention group or PregnancyPlus attention control group. In the event that group prenatal care is not feasible, the group sessions can be conducted as virtual visits (using programs such as Zoom, WebEx, Facetime etc.) or content can be provided in a 1:1 patient to provider setting. Different care providers will deliver the COPE-P and PregnancyPlus content, assuring that there is no carryover effect of the intervention into the control group. [name] will conduct the training of the attention control group midwives and [name] will conduct the training of the intervention group midwives. The same protocol for assessing fidelity will be used for COPE-P and PregnancyPlus. [name] will train the research team to assess fidelity of the intervention with the intervention fidelity checklist. Fidelity will be assessed by having research team members observe 2 of the 6 sessions for each intervention group. Inter-rater reliability of 90% will be established and observer drift monitored and corrected throughout the trial. Feedback will be provided immediately after the session to interventionists if they are not adhering to the intervention as intended to be delivered.

At the end of the 18-week timeframe and at their last group prenatal care session, all women will complete the GAD-7, PSS, EPDS, a 24 hour diet recall, the Healthy Lifestyle Behaviors Scale and the Healthy Lifestyle Beliefs Scale. Fitbit data and weight also will be obtained. In the intervention group, participants also will complete the COPE-P evaluation. This data will be **T1**, and will be collected at approximately 31 weeks gestational age. For women who miss this visit, data will be collected at the next scheduled prenatal visit. Participants will be compensated \$30 for their study participation.

Data collection at the 3 month post intervention follow up visit, **T2**, will occur at the normally scheduled 4-6 weeks regular postpartum visit. Participants will be compensated \$40 for their study participation at this visit. All measures will be collected.

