For all continuous outcomes, such as anxiety, the basic model, to which we can add our controls and predictors. The level 1 submodel estimates how each participant's anxiety changes over the four data collection periods. The level 2 submodel will relate the inter-individual differences to intervention group and other time-invariant predictors and controls, such as medication (i.e., antidepressants) and have begun therapy (i.e., in usual care for mental health diagnoses), and will estimate a participant's initial anxiety level and rate of change in anxiety. Anxiety will be modeled in terms of random subject effects (intercept and time trends) to account for individual differences in how participants change over time. We will begin with a linear model for time but will investigate nonlinear effects as suggested by the data. Subsequent models will contain time-varying covariates (i.e., dose of intervention, weight, exercise) and thus will focus on within-participants effects, that is, whether within-participant differences in the covariates are associated with within-participant differences in anxiety. We will examine the potential of cognitive beliefs and perceived difficulty in leading a healthy lifestyle in mediating the effects of the COPE-P program on healthy lifestyle behaviors and psychological symptoms. Rather than detecting mediated effects with the causal steps approach of Baron and Kenny, we will use the Joint Significance Test established by MacKinnon, which assesses the statistical significance of the X to M relation,  $\alpha$  path, and then the M to Y relation,  $\beta$  path. If both are statistically significant, there is evidence of mediation. Models with more than one mediator are simply extensions of the single-mediator case. In our multilevel models, we will investigate mediation effects within the different levels of analysis and across levels. Finally, we will explore characteristics that may moderate healthy lifestyle behaviors, psychosocial health, and birth outcomes (e.g., race/ethnicity, age, parity, language spoken, level of education, income, marital status) in the above models. The proposed examination of mediators and moderators should allow for increased understanding of mechanisms underlying any intervention effect and different responses among the participants. The most appropriate covariance structure for the residuals  $\epsilon_{ij}$  will be determined after data collection and the correlation of responses over time is estimated. Several covariance structures will be examined and the resulting models compared for fit using the quasi-likelihood independence model information criterion (QIC) fit using SAS 9.4 (Proc MIXED).

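### Midwives are nested in arm and no described model contains midwife or prenatal-care group, so standard errors for the COPE-P effect are too small if outcomes cluster by midwife

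*Combined protocol and SAP*

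**What the plan says.** The paragraph on the PregnancyPlus Attention Control Group separates the providers by arm: "Different care providers will run the COPE-P and PregnancyPlus groups, assuring that there is no carryover effect of the intervention into the control group". The Procedure section repeats this ("Different care providers will deliver the COPE-P and PregnancyPlus content") directly after allowing virtual or one-to-one delivery. Each arm's midwives are trained separately.

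The unit of allocation is the prenatal-care group (Overview of the design): "Each group within the 18-week time segment will be randomly assigned (using a sealed envelope technique) as either a COPE-P or PregnancyPlus group". The same section says "There will be a total of 30 groups over the course of the study", and that in each segment at Jacobi "there will be two control groups and two intervention groups". The only staffing figure is under Setting: "Obstetrical care is provided by 22 licensed midwives at Jacobi Medical Center as well as by over 40 obstetricians". How many midwives lead study groups, how many groups each leads, whether leadership is shared, and how midwives are assigned to arms are not stated. No count is given for the Ohio site.

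In the Analysis plan, the continuous-outcome model has time within participant at level 1 and participant at level 2; its random effects are for participants only (the wording is "random subject effects (intercept and time trends"). The logistic model has one error term per participant. The t-tests and (repeated-measures) ANCOVA listed for the primary outcomes have no cluster term either. The named covariates are medication, therapy, dose, weight and exercise.

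**The concern.** Separate providers are a reasonable guard against carryover, but no midwife then appears on both sides of the comparison, so any difference between midwives falls between the arms. Baseline is taken before the sessions, so an influence of the midwife can only appear afterwards. It then enters the arm-by-time term, which the plan treats as the test of effectiveness. Random intercepts and slopes for each woman still treat women as independent of one another and do not capture change shared by one midwife's participants.

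This is a level above the prenatal-care group. A random effect for group would treat two groups led by one midwife as independent. Under the one-to-one fallback the group disappears as a unit of delivery, but the midwife remains a cluster.

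Anxiety, stress and depressive symptoms are primary outcomes on which the individual provider could plausibly matter. At stake are false-positive risk and confidence intervals that overstate precision.

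**Working it through.** **The plan's own figure.** Sampling claims more than 80% power with 364 completers for an effect printed as 25, read here as 0.25 SD (an assumption). A two-sided comparison of two means with 182 per arm gives 66.5%. ANCOVA on the mean of T1 to T3, with an assumed within-person correlation of 0.5, gives 95.9%. The claim thus depends on an unstated correlation and is neither confirmed nor refuted. Both calculations assume independent women.

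**Are repeat leaders forced?** With one leader per group and all 30 groups at Jacobi, 30 − 22 = 8 groups at least have a leader who has already led one (average 30/22 = 1.36 groups per midwife). Spread evenly, 14 midwives lead one group and 8 lead two. The Jacobi reading fits the stated minimum of six women per group (182/30 = 6.1 completers, 236/30 = 7.9 enrolled) but is not stated. If the 30 groups covered both sites equally, about 15 would be at Jacobi and no repeat would be forced.

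**Participant-level test, midwife ignored.** Inputs: 182 completers at Jacobi, so 91 per arm at 1:1; K midwives per arm and provider ICC, both assumed. Women per midwife m = 91/K; design effect DE = 1 + (m − 1) × ICC; the standard error should be √DE times larger; true type I error = 2Φ(−1.96/√DE).

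| Midwives per arm | m | ICC .01: DE, type I | ICC .03: DE, type I |
|---|---|---|---|
| 11 (all 22 used) | 8.3 | 1.07, 5.8% | 1.22, 7.6% |
| 8 | 11.4 | 1.10, 6.2% | 1.31, 8.7% |
| 3 | 30.3 | 1.29, 8.5% | 1.88, 15.3% |

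With K = 3 and ICC .03, for example: DE = 1 + 29.3 × .03 = 1.88 and √1.88 = 1.37, so the standard error should be 37% larger. The result depends on K only through m. Two sites with 182 per arm and twice as many midwives give the same figures.

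**What remains once group is modelled but midwife is not.** Take ICC .02, six women per group, 15 groups per arm, and no separate group variance. The provider's share of the variance of a group mean is .02/(.02 + .98/6) = .109. With g groups per midwife, DE = 1 + (g − 1) × .109.

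- 3 midwives per arm: g = 5, DE 1.44, type I error 10.2%.
- 8 per arm: g = 1.9, DE 1.10, 6.1%.
- 11 per arm: g = 1.36, DE 1.04, 5.5%.

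**Power when midwife is modelled.** Both sites, 182 per arm, 0.25 SD, here with ICC .01 to .05. Noncentral t with 2K − 2 degrees of freedom and noncentrality 0.25/√(v × DE × 2/182). For the simple comparison v = 1; for ANCOVA on three follow-ups at correlation 0.5, v = (1 + 2 × 0.5)/3 − 0.5² = 0.417.

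- 22 midwives per arm: 51% to 61% simple (against 66.5%), 87% to 94% repeated measures (against 95.9%).
- 4 per arm: 20% to 39% simple, 41% to 73% repeated measures.

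**The case against.** The strongest reply is that the size is unknown and may be small. Neither the ICC nor the number of study midwives is documented. If all 22 Jacobi midwives took part, inflation is modest, and about 5.5% once group is modelled. Much of the inflation arises because the randomised unit, the prenatal-care group, is also missing from every model. If each midwife led one group, the two levels would coincide and a group effect would suffice. All of this stands, and it limits the point.

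The plan also applies one fidelity protocol to both arms: observation of 2 of 6 sessions, 90% inter-rater reliability and immediate feedback. This may reduce differences in delivery. It does not equalise the skill of midwives, and it does not enter the variance of the estimate.

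The plan speaks generally of adding controls and of mediation at different levels of analysis. Neither names a provider level.

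Two stronger readings are tempting and are not supported. A reader might infer that every midwife must lead more than one group; 30 groups against 22 midwives forces only some repeats, and only on the Jacobi, one-leader reading. A reader might also reach a type I error of 24%. That needs 182 women per arm shared among 3 midwives across both sites at ICC .03 (DE = 1 + 59.7 × .03 = 2.79), about 1.5 midwives per arm per site. Nothing in the documents points to so few.

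**Conclusion.** The point holds in conditional form. Nesting of midwives in arm and the absence of midwife and group from the described models are facts of the plan. That the standard errors are too small follows if provider ICC exceeds zero. On the Jacobi basis with ICC .01 to .03, a nominal 5% test runs at about 6% to 15% across 11 down to 3 midwives per arm; with a group effect in the model, at about 5.5% to 10% (ICC .02). These ranges rest on assumed ICCs and staffing, 1:1 allocation, equal numbers of women per midwife and one leader per group.

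It would also go too far to conclude that a midwife random effect settles the matter. It reflects chance differences between midwives. Systematic differences, such as how midwives were chosen for an arm or the separate training, stay inseparable from the arm effect in any model. The documents do not show that such a difference exists; they leave the allocation of midwives undescribed.

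**What to change.** - Record the group identifier and lead-midwife identifier for every participant, with all leaders where leadership is shared and the delivering midwife under one-to-one delivery. If this is not captured during delivery, it may not be recoverable.
- Fit random effects for group within midwife, with midwife nested in arm and site, using Kenward-Roger or Satterthwaite degrees of freedom. Where midwives are too few to estimate this, make it a pre-specified sensitivity analysis.
- Report the number of midwives per arm and site, the groups each led, and how they were allocated to arms.
- Allocate midwives not yet trained to arms by lot within site and language. Where that is no longer possible, limit the conclusion to COPE-P as delivered by these midwives.
- Restate power under a stated range of ICCs and midwife numbers.

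Separate providers per arm can stay. The cost is two identifiers, analysis plan wording and, where still possible, the organisation of the draw. The downside is wider intervals and lower power, substantially lower if only a few midwives lead all the groups.

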At eight months post intervention (**T3** - six months postpartum at the six-month well baby visit), all women will once again be contacted and complete all measures (including weights taken on available pediatric clinic adult scales –same model as prenatal scales). Participants will receive \$50.00 for their participation. Outcome data from charts will be collected by team members blind to group assignment.

If study visits cannot be conducted face-to-face, data will be collected through telehealth methods such as via phone or video call (Zoom or Facetime etc.).

**Sampling.** Women will be recruited from the antenatal clinic if they are: between 18 and 40 years old, in their first trimester with an uncomplicated singleton pregnancy of less than 19 weeks, and self-identify as either Black or Hispanic and can read and speak English or Spanish. A completed sample size of 182 Black and Hispanic women from JMC in the Bronx and 182 Black and Hispanic women from OSU Total Health and Wellness clinics will be required to meet the determined sample size of 364 total (at 4 data collection points for each, resulting in ~1,450 observations). This will have greater than 80% power to detect small to moderate effects (i.e. 25 or greater) between group differences in healthy lifestyle behaviors, psychosocial health, and outcomes testing at alpha = .05 for all proposed models. The sample of 364 will have > .80 to detect a small to medium mediated effect. The sample of 364 will have > .80 to detect a small to medium mediated effect.

**Setting. Jacobi Medical Center** is part of New York City Health + Hospitals (NYC H + H), the largest municipal hospital system in the United States. New York City Health + Hospitals oversees the public health care system in all the five boroughs that comprise New York City. It provides one-fifth of the total number of discharges and more than one-third of the emergency services and hospital-based clinic visits in all of New York City. Jacobi Medical Center is an academic affiliate of the Albert Einstein College of Medicine. Jacobi Medical Center is located in the Bronx. As one of the largest health care delivery facilities in the Bronx and in New York City, Jacobi Medical Center has developed a world- wide reputation of distinction. It is renowned for its primacy in

07/30/2021

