**Hypothesis-driven analyses.** Various bivariate tests (e.g., independent and dependent t-tests, correlations, ANCOVA and repeated measures analyses of covariance) will be used to evaluate differences and longitudinal patterns of change across time and between relevant subgroups (e.g., intervention groups, language groups) for each significant outcome in the preliminary bivariate analyses, (primary outcomes are healthy lifestyle behaviors, anxiety, stress, and depressive symptoms). For secondary outcomes (appropriate weight gain during pregnancy, birth and post-natal outcomes (e.g., mode of delivery, birth weight/length, gestational age, postpartum weight loss and breastfeeding practices) we will fit a series of longitudinal multilevel growth models to the data.

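### If the effect size is a standardised mean difference of 0.25, the claim of more than 80% power for every proposed model is not met: unadjusted single-visit and once-only continuous outcomes have 66%, with 0.29 SD detectable at 80%

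*Combined protocol and SAP*

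**What the plan says.** The Sampling paragraph sets the "determined sample size of 364 total (at 4 data collection points for each, resulting in ~1,450 observations") and continues: "This will have greater than 80% power to detect small to moderate effects (i.e. 25 or greater) between group differences". The claim covers lifestyle behaviours, psychosocial health and outcomes, "testing at alpha = .05 for all proposed models". A separate sentence, printed twice, says: "The sample of 364 will have > .80 to detect a small to medium mediated effect". No metric, sidedness, correlation, test or formula accompanies either statement.

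The analyses to which the claim must apply are varied:

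- **Hypothesis-driven analyses** lists "Various bivariate tests (e.g., independent and dependent t-tests, correlations, ANCOVA and repeated measures analyses of covariance"), and Hypothesis 1a predicts a difference at each of three post-intervention times.
- **Table 1** shows birth weight and gestational age, both Hypothesis 1b outcomes, as taken from the chart once, after delivery.
- **The basic model for continuous outcomes** is longitudinal over four visits, starting with linear time. The paragraph on dichotomised outcomes names the group-by-time interaction as the test of effectiveness.
- **The covariance structure** is left to be settled after data collection.

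**The concern.** A claim about all proposed models fails if one of them falls short. The roughly 1,450 observations look like the basis for the power, but repeated visits add nothing where each woman contributes one value and no baseline is used. That is the case for an independent t-test at T1, T2 or T3, and for birth weight and gestational age, which have neither a baseline nor a repeat.

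What is at stake is how a null result is read. On the stated power, a non-significant birth-weight or single-visit comparison would count as fair evidence against a 0.25 SD effect. At 66% power, such an effect would be missed about one time in three.

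**Working it through.** **Inputs.** There are 364 completers (Sampling). Allocation is 1:1, since in each time segment "there will be two control groups and two intervention groups", so 182 per arm. Alpha is .05. *Assumptions:* the test is two-sided; the effect is a standardised mean difference d = 0.25; the within-person correlation r is equal between all visits and ranges from .3 to .7. Attrition is not applied, because 364 is already the completed sample.

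**1. The plan's own figure, one value per woman, unadjusted.** The expected test statistic is d × √(n/2) = 0.25 × √91 = 2.385.
- Two-sided power, noncentral t with 362 df: 66.2% (normal approximation 66.5%).
- One-sided: 77%.
- Effect detectable at 80%, two-sided: (1.960 + 0.842) × √(2/182) = 0.294 SD.
- Size needed for 80% at 0.25 SD: 252.1, so 253 per arm.

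The stated figure of more than 80% is not reproduced for these comparisons.

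**2. Other readings of the effect size.** Cohen's f = .25 is d = 0.5, and gives power above 99%. A correlation of .25 also gives more than 99%. On either reading about 125 to 130 women would be enough for 80%.

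**3. Models that use baseline or repeated values, d = 0.25, 182 per arm.** Each row takes an outcome variance relative to a single visit. Row 1 uses the noncentral t and the others the normal approximation.

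| Analysis | Relative variance | r = .3 | r = .5 | r = .6 | r = .7 |
|---|---|---|---|---|---|
| Single-visit ANCOVA on T0 | 1 − r² | 70% | 78% | 84% | 91% |
| Unadjusted mean of T1–T3 | (1 + 2r)/3 | 90% | 83% | 80% (79.5) | 76% |
| T0-adjusted mean of T1–T3 | (1 + 2r)/3 − r² | 95% | 96% | 97% | 99% |
| Linear group × time, 0.25 SD from T1 onward | (1 − r)/5, slope 0.075 | 48% | 62% | 72% | 83% |

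For the last row, visits are scored 0 to 3, so the centred scores are −1.5, −0.5, 0.5 and 1.5, with sum of squares 5. Differences of 0, .25, .25 and .25 project to a slope of (−0.5 + 0.5 + 1.5) × 0.25 / 5 = 0.075. At r = .5, z = 0.075 / √(2 × 0.1/182) = 2.26, giving 62%. If the difference instead builds linearly to 0.25 SD at T3, power at r = .3, .5, .6 and .7 is 57%, 71%, 80% and 90%.

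Single-visit ANCOVA reaches 80% from about r = .53.

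**4. Clustering, for scale only.** With an assumed group size of 6 and an assumed intraclass correlation of .01 to .05, the design effect 1 + 5 × ICC is 1.05 to 1.25. The 66% then falls to 64% to 57%, and the detectable effect rises to 0.30 to 0.33 SD.

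**The case against.** The strongest reply is that the metric is unstated. ANCOVA, repeated-measures ANCOVA and correlations are among the listed analyses, and f or r is a usual scale for them; on either, the claim is true. That 364 would then be far more than needed is not decisive, because the claim is a floor and the same sample also serves the mediation aim. This stands as a limit on the finding. The standardised-difference reading fits the plan's description of a small to moderate difference between groups, but it is an inference. The missing decimal point may come from text extraction and carries no weight here.

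Second, the plan is mainly longitudinal, and repeated or baseline-adjusted analyses can exceed 80%. This also stands. A reader might infer that the trial is underpowered for most of its tests, or that only the T0-adjusted average meets the claim. The table supports neither: ANCOVA passes from about r = .53, the unadjusted T1–T3 mean passes at r = .3 and .5, and the interaction passes at r = .7. T0 values carry no treatment contrast themselves but raise power through adjustment.

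Third, a reader might infer that mediation power is capped at 66%, because the joint significance test needs the arm effect on beliefs to be significant. That cap would hold only for an unadjusted single-visit test of a 0.25 SD effect. Beliefs are measured at T0 to T3 and mediation is to be examined in multilevel models, so the cap is not established. Joint power with 364 women runs from about 59% with both paths at .14 to above 99% with both at .26. The mediation claim is unsupported as written, not refuted.

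None of this rescues the extension to every model. Birth weight and gestational age gain nothing from repeats or a baseline, whatever the correlation.

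**Conclusion.** The concern holds, conditional on reading the effect as 0.25 SD. With 182 completers per arm and two-sided alpha .05, power is 66% for an unadjusted single-visit comparison and for a continuous outcome recorded once; 80% power is reached at 0.29 SD. One-sided testing (77%) does not close the gap. These figures make no allowance for prenatal-group clustering, which would lower them. The remaining models lie above or below 80% according to a correlation that the documents leave open. The error is therefore in the scope and specification of the power statement. It does not show that 364 women are too few for the repeated-measures comparisons.

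**What to change.** In the Sampling paragraph:

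- State the effect-size metric (and correct the figure if a decimal point is missing), the sidedness, the test and the assumed within-person correlation.
- Delete the extension of the claim to all proposed models.
- State that, for unadjusted single-visit comparisons and continuous outcomes recorded once, 182 completers per arm give 80% power for 0.29 SD and 66% for 0.25 SD, and that clustering by prenatal group would lower this.
- Limit the claim of more than 80% at 0.25 SD to the repeated-measures or baseline-adjusted analyses that reach it at the stated correlation, and name them.
- For mediation, give the assumed sizes of both paths and the model behind the figure. Do not substitute a minimum arm effect on beliefs: power for that path alone does not fix joint power.

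This changes wording only. No extra women are needed and no procedure changes. The one cost is a less favourable stated figure for some outcomes.
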